5.2. Data Conventions

The following conventions will be used:

- **Period definition:**
 - **Screening Period:** The period prior to Day 1 visit.
 - **Treatment and Observation:** The period from date of vaccine administration to Day 29 visit.
 - **Follow-up:** The period from Day 29 visit to Month 6 visit.
- **Visits:**
 - **Study day 1:** The date of study vaccine administration.
 - **End of Treatment Visit:** The Day 29 visit, or the early discontinuation visit for subjects who withdraw study prior to Day 29.
 - **End of Study Visit:** The last recorded visit date.
 - **Unscheduled visits:** Unscheduled visits results will be listed, but not included in tables or graphs. Rules to map unscheduled visit to analysis visit are defined in Section 5.5.
- **Conversion factors (for derived data calculations):**
 - 1 month = 30.4375 days
 - 1 week = 7 days
- **Baseline characteristics and change from baseline:**
 - Weight values recorded in pounds will be converted to kilograms using the following formula: kilograms = pounds/2.2046.
 - Height values recorded in inches will be converted to centimeters using the following formula: centimeters = inches*2.54.
 - Duration on study (weeks) = (Last visit date – randomization date + 1) / 7.
 - (Absolute) Change from baseline = Value at the time point – Baseline value.

[figure not shown]
- **Adverse events:**
 - **Solicited Adverse Events** will be analyzed using the nominal visit (i.e. the page) on which they were recorded and not according to the date they were entered.
 - **Solicited Adverse Events continuing beyond 7 days:** Solicited AEs continuing beyond 7 days will be reported in the “Adverse Evens (Unsolicited)” page as per Case Report Form (CRF) Completion guidelines and will be identified programmatically as all unsolicited adverse events with answer ‘Yes’ to the question ‘Is this a continuing solicited adverse event?’. The corresponding question in the diary page will not be checked programmatically as it is expected that both sources will be reconciled before DBL so that only the unsolicited page can be used for this analysis.
- **Immunogenicity:**
 - **GMC [or GMT]:** The geometric mean concentration (or titer) = antilog (LSMeans [log₁₀ x]), where x is the assay result and LSMeans is the least square means calculated by the model.

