6.4.1. Adverse Events

6.4.1.1. Solicited Adverse Events

Solicited AEs are protocol-specified local and systemic symptoms/events that are proactively collected from the subject and evaluated by the Investigator or designee. Solicited AEs are collected for 7 days after each injection, starting on Day 1, within an electronic diary.

Solicited AEs for this study are:

- Local events: Pain, Erythema (redness) at the injection site, Edema (swelling) at the injection site
- Systemic events: Fever (oral temperature $\geq 100.4^{\circ}\text{F}$), Fatigue, Headache, Muscle pain, Joint pain

The Subject and the Investigator will grade all AEs for severity from "mild" (grade 1) to "potentially life-threatening" (grade 4), except for severity of redness and swelling recorded as diameters (cm) and graded accordingly (see Guidance for Industry Toxicity Grading Scale for Healthy Adult and Adolescent Volunteers Enrolled in Preventive Vaccine Clinical Trials, September 2007 for details on grading scale).

Only Solicited AEs collected in the diary CRF, within 7 days after vaccine administration (i.e. from Day 1 to Day 7) will be analyzed in this Section. Occurrence of a solicited AE on a specific Day will be identified by a Grade ≥ 1 for that AE on that day.

Solicited AEs continuing beyond 7 days after injection will be combined with unsolicited AEs and described separately as specified in Section 6.4.1.3.

The following characteristics will be calculated:

- Maximum severity (Investigator):

For each solicited AE collected for a subject, the maximum severity will be the highest grade recorded, as per Investigator, for all occurrences of this AE within 7 days of vaccine administration (i.e., from Day 1 post-administration to Day 7) for the overall summary, or within a single day for the summary by day. There will be no replacement in case of missing severity.

- Maximum relationship (Investigator):

For each unsolicited AE collected for a subject, the maximum relationship will be the strongest relationship, as per Investigator, for all occurrences of this AE. There will be no replacement in case of missing relationship.

- Time of first onset of first event (days):

Day of onset of the first solicited AE, as per the nominal visit where the first solicited AE was first reported (as per Investigator). This will range from 1 (Day 1 = Day of study vaccine administration) to 7 (Day 7).

- Duration of solicited AEs (days):

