Number of days between the onset of the solicited AE (i.e. nominal visit of first occurrence of Grade \geq 1) and the end of the solicited AE (i.e. nominal visit when Grade is back to 0).

If there are different occurrences of a same solicited AE within 7 days, the durations will be added up.

For solicited AEs continuing beyond 7 days, the end day of the continuing event will be used as end day for the calculation.

Example: If a subject has a Fatigue starting on Day 2 and finishing on Day 3. And a new Fatigue starting on Day 7 and ending on Day 9. The Duration will be 1+2=3.

If the solicited AE is ongoing (i.e. stop date is missing), then duration will be the Number of days between the onset of the solicited AE and the study discontinuation date.

Frequencies and percentages of subjects experiencing each solicited AE will be presented overall and by severity. For each of the time points or time intervals presented in the summaries, only subjects with at least one observation (i.e., any non-missing values but excluding "Not done/unknown") for the solicited AEs will be summarized.

The following summaries of subjects will be performed:

- Solicited AEs within 7 days post-injection, for each event and for any event, overall and by maximum severity. Details by category (local, systemic) will also be presented. (Severity as per Investigator)
- Solicited AEs by day post-injection, for each event and for any event, overall and by severity. (Severity as per Investigator)
- Solicited AEs by day post-injection, for each event and for any event, overall and by severity. (Severity as per Subject)

- Time of first onset of solicited AEs within 7 days post-injection for each event and any event. Duration of each solicited AEs and maximum duration for any event. (Severity as per Investigator)

Listings of all solicited AEs will be provided by subject.

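### Solicited AEs with no stop date are counted as lasting to study discontinuation (about 174 to 180 days for a completer) and pooled with observed durations

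*SAP*

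**What the plan says.** The duration rule in SAP 6.4.1.1 has three parts.

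- **Diary events.** Duration runs from the first diary day at Grade 1 or more to the "nominal visit when Grade is back to 0". The diary window is short: "Only Solicited AEs collected in the diary CRF, within 7 days after vaccine administration (i.e. from Day 1 to Day 7) will be analyzed".
- **Events that outlast the diary.** "For solicited AEs continuing beyond 7 days, the end day of the continuing event will be used as end day for the calculation". SAP 5.2 identifies these events by a flag on the unsolicited AE page. The diary page has a matching question, and "it is expected that both sources will be reconciled before DBL". The worked example includes such an event: "And a new Fatigue starting on Day 7 and ending on Day 9. The Duration will be 1+2=3".
- **Events with no stop date.** These are called ongoing, and "then duration will be the Number of days between the onset of the solicited AE and the study discontinuation date". SAP 6.1.6 adds that stop dates are never imputed.

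The planned outputs are the duration of each solicited AE and the maximum duration of any event. SAP 6.1.1 summarises continuous variables by mean, median, standard deviation, minimum and maximum.

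**The concern.** The third part turns a time that is censored, or simply unknown, into an observed duration. It sets no cap, no censoring flag and no separate count of the events it affects.

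Its end date is also unclear. Under Protocol 5.18, discontinuation means leaving before the Month 6 call, so a completer has no discontinuation date. SAP 5.2 defines an End of Study Visit, but the duration rule does not use it.

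Missing stop dates are plausible. Protocol 7.4 lets follow-up of an AE end when the condition stabilises, ceases to matter clinically, or the subject is lost, and none of these guarantees a stop date. Under Protocol 6.1.5 the Month 3 and Month 6 calls schedule only SAE, NOCI and MAAE evaluation. A mild fatigue still open at Day 29 therefore has no scheduled recheck, yet would be counted to about Month 6.

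The first part leaves a smaller gap. An event at Grade 1 or more on Day 7 has no later diary grade. If it is not flagged as continuing, no part of the rule clearly gives it an end day.

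What is at stake is a descriptive tolerability table, in which two dose groups could appear to differ because of one record.

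**Working it through.** **1. Reproduce the SAP's example.** Duration = end day − onset day, summed over occurrences. Day 2 to Day 3, plus Day 7 to Day 9: (3 − 2) + (9 − 7) = 1 + 2 = 3 days, as the SAP states. Counting both end days would give 2 + 3 = 5, so the convention is simple subtraction.

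**2. Locate Month 6 on the study-day scale.** Protocol 6.1.5 puts the call 180 days after Day 1, ± 5 days, which is study day 181 (176 to 186). This agrees with Protocol 3.3: 30 screening days + 181 study days = 211.

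**3. Apply the missing-stop-date rule to a completer**, assuming the end date is the Month 6 contact. SAP 6.4.1.1 allows onset from Day 1 to Day 7.

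- Onset Day 1: 181 − 1 = 180 days (175 to 185 with the window).
- Onset Day 7: 181 − 7 = 174 days (169 to 179).

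The range is 174 to 180 days at the nominal date and 169 to 185 overall. For a subject who leaves early the value is shorter.

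**4. Effect on an arm's mean.** SAP 2.3 plans 50 subjects per arm. Let m be the number in the arm with the event. Assume m − 1 of them have 2 days and one has 174:

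mean = ((m − 1) × 2 + 174) / m

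| m | Calculation | Mean (days) | Mean without the record |
|---|---|---|---|
| 10 | (18 + 174) / 10 | 19.2 | 2.0 |
| 20 | (38 + 174) / 20 | 10.6 | 2.0 |
| 30 | (58 + 174) / 30 | 7.7 | 2.0 |
| 40 | (78 + 174) / 40 | 6.3 | 2.0 |

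Using 169 or 185 days instead of 174 gives 10.3 to 11.2 at m = 20. The maximum becomes the outlying value itself. In this illustration the median stays at 2 days.

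**5. The unflagged Day 7 event.** With Day 8 as its end day, an event that starts on Day 7 lasts 8 − 7 = 1 day. If the lack of a stop date were read as ongoing, it would last 174 days (169 to 179). The SAP does not say which applies.

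**The case against.** Three stronger readings are tempting, and the documents do not support them.

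- *A reader might infer that no event present on Day 7 has an end day.* The SAP gives one to events continuing past Day 7, and its example starts on Day 7. Only unflagged events are left out.
- *A reader might infer that a brief Day 7 reaction will be tabulated as lasting months.* That requires applying the missing-stop-date rule to a diary-only event. Such an event is defined by daily grades, and the reconciled flag says that it did not continue. The SAP neither states nor excludes this reading.
- *A reader might infer that continuing events are counted one day short and need a day added to the stop date.* The example subtracts in the same way for both types. Adding a day would turn 9 − 7 = 2 into 3 and contradict the SAP's total.

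The best case for leaving the rule alone is that few records will trigger it. The diary is reviewed at Day 8 and AEs again at Day 29, AEs are followed up, and queries are resolved before study completion. Those left without a stop date should mostly be truly ongoing, so a long value is not absurd. The median is already planned, and by-subject listings would show the outlier. The primary endpoints are percentages of subjects, and SAP 6.1.1 confines formal testing to immunogenicity.

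All of this stands as a limit on importance. It does not make the pooled figure right. For an event last confirmed at Day 29 with no recheck, the time to Month 6 was not observed, and an event that is truly ongoing has a censored duration, which a plain mean treats as complete.

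**Conclusion.** The point holds as a minor one. A stated rule assigns 174 to 180 days (169 to 185 with the visit window) to a completer's solicited AE with no stop date and pools that value with observed durations. One such record is enough to dominate the mean and maximum in an arm of 50.

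The day range assumes that a completer's discontinuation date is read as the Month 6 contact; read literally, completers have no end date at all. The shifts in the mean also assume 2 days for every other affected subject and a chosen number affected. The documents give neither figure, nor how often stop dates will be missing.

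The missing end day for an unflagged Day 7 event is a definite gap in the text, but its consequence is uncertain. No primary endpoint is affected.

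**What to change.** In SAP 6.4.1.1 and the programming specification:

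- **(a)** Exclude events without a stop date from the mean and maximum, or treat them as censored at the last contact at which the event was confirmed present. In either case, report their number by arm as ongoing.
- **(b)** Where an end date is needed for a completer, use the End of Study Visit date already defined in SAP 5.2 in place of the study discontinuation date.
- **(c)** Set Day 8 as the end day for an event at Grade 1 or more on Day 7 that is not flagged as continuing.

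The subtraction convention and the planned medians can stay as they are.

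The cost is a few lines of text and code, with no new data. The drawback is that some events will have no numeric duration. If they are excluded, truly long events leave the mean, so the count of ongoing events must appear beside it.

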6.4.1.2. Unsolicited Adverse Events

An unsolicited AE is an AE that is spontaneously reported by the subject or discovered by the Investigator. SAEs, NOCIs and MAAEs would be recorded as part of the collection of unsolicited AEs as specified in the visit procedures. Unsolicited AEs are collected separately from solicited AEs.

Solicited AEs continuing beyond 7 days will be flagged using rules given in Section 5.2 and described in separate summaries as explained in Section 6.4.1.3.

The definition of a treatment emergent AE (TEAE) is an event that occurs after vaccination and within the 28 days after vaccination (i.e., excluding those after a subject has given informed consent, but before vaccination):

- Onset (days) = Start date of AE – Date of Study Vaccine Administration + 1
- An AE is a TEAE if Onset \geq 1 and Onset \leq 28

Adverse events are summarized by subject, therefore, in any tabulation, a subject contributes only once to the count for a given adverse event (SOC or preferred term).

Unsolicited AEs will be coded using the Medical Dictionary for Regulatory Activities (MedDRA) and will be summarized by decreasing frequency of SOC and preferred term within SOC in the control group, as follows:

- Any unsolicited TEAEs
- Possibly or probably related unsolicited TEAEs
- Unsolicited TEAEs leading to study withdrawal
- Any AE leading to death
- Any SAE within 6 months after the vaccination by maximum relationship to study treatment. This summary will include serious solicited AEs.
- Any NOCI within 6 months after the vaccination by maximum relationship to study treatment.
- Any MAAEs within 6 months after the vaccination by maximum relationship to study treatment.

Following by-subject Listings will be provided:

- Pre-vaccination AEs (non-emergent)
- All unsolicited TEAEs
- All post-vaccination SAEs, NOCIs and MAAEs

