3 STUDY PLAN

3.1 Study Design

[figure not shown]
This Phase 2, randomized, observer-blind study is to be conducted in healthy adults aged 65 and older. Subjects may screen for up to 30 days prior to randomization however, they may be screened and randomized within the same visit. Demographics, medical history, and concomitant medication use will be collected. Subjects will be randomly assigned in a 1:1:1:1 ratio to receive either VAX-24 at one of three dose levels or the active comparator.

Subjects will receive VAX-24 or PCV20 on Day 1. Solicited AEs will be collected for 7 days post-vaccination via diary and unsolicited safety information for 28 days post-vaccination, with SAEs, NOCIs, and MAAEs collected up to 6 months post-vaccination. All subjects will have blood samples drawn for immunogenicity analysis (OPA and IgG) at Days 1 and 29. A Data Monitoring Committee (DMC) will be adjudicated for the study. If the study meets a pre-defined stopping criterion, the study will be paused, and data reviewed by the DMC prior to re-starting the enrollment.

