3.3 Estimated Study Duration

The Screening period is up to 30 days, treatment and observation period is from Day 1 to Day 29, and the follow-up period is through Month 6 post study vaccination. The maximum possible study duration for an individual is 211 days.

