6.1.4 Day 29 (\pm 3 days)

The following procedures will take place during this visit:

- Review of concomitant medications
- AE (unsolicited) and SAE evaluation
- Blood collection for serum sample for immunogenicity

6.1.5 Months 3 and 6 (90 to 180 days after Day 1 (\pm 5 days))

These visits are follow-up phone calls for safety evaluation. The following procedures will take place at each visit:

- SAE, NOCI, and MAAE evaluation
- Review of concomitant medications associated with SAEs, NOCIs, MAAEs, or prohibited medications

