7 SAFETY

7.1 Definitions

7.1.1 Adverse Event

An adverse event is any untoward medical occurrence in a study subject, regardless of the suspected causal relationship with study vaccine.

The definition of an AE includes:

- A new-onset symptom or disease
- An exacerbation of a pre-existing symptom or disease
- A new-onset laboratory abnormality considered by the Investigator to be clinically significant
- A new-onset symptom or disease that occurs as a result of a protocol-specified procedure

The definition of an AE does **not** include:

- A pre-existing symptom or disease that does not worsen during the study (even if first disclosed by the subject after the start of the study)
- A medical or surgical intervention such as surgery, endoscopy, tooth extraction, or transfusion (although the condition leading to the procedure or a complication from the procedure may be an AE)
- An uncomplicated pregnancy
- A dosing error without any resulting signs or symptoms
- Any other situation where an untoward medical occurrence has not occurred (eg, hospitalization for cosmetic elective surgery or social admissions)

The definition of a treatment emergent AE (TEAE) is an event that occurs after vaccination and within the 28 days after vaccination (ie, excluding those after a subject has given informed consent, but before vaccination).

The definition of a NOCI includes:

A new onset of chronic illness is a disease or condition, which is newly diagnosed, requires ongoing medical attention and/or limits activity of daily living (eg, heart disease, cancer, diabetes).

The Investigator will attempt to establish a diagnosis based on signs, symptoms, and other clinical information. Whenever possible, the Investigator will report an AE as a diagnosis rather than one or more signs or symptoms. If a clinically significant laboratory abnormality meets the

definition of an AE, a diagnosis or clinical signs and symptoms rather than the abnormal laboratory finding should be reported if possible. If no diagnosis is known and clinical signs and symptoms are not present, but the laboratory abnormality is clinically significant by itself, then it should be reported as the AE.

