7.5.1 Reporting Periods

The four reporting periods for solicited AEs begin immediately after study vaccine administration and continue for 7 days after the injection. The reporting period for unsolicited AEs is immediately after study vaccine administration on Day 1, continuing through Day 29. AEs that correspond to solicited AE terms but occur outside of (or continue past) the solicited AE collection periods are also collected through the unsolicited AE reporting periods. The reporting period for SAEs begins at the time of informed consent and continues for the duration of study participation.

A summary of the reporting periods is presented in Figure 2.

Figure 2 Safety Events Reporting Periods

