9.2 Treatment Period

The Treatment period begins at the time of study vaccine administration and extends through the Day 29 visit. The Follow-up period spans the time following the Day 29 visit through Month 6 (after study vaccine administration).

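### The SAP's treatment-emergent window ends on Study Day 28, one day before unsolicited AE collection ends, so some Day 29 AEs reach no planned table or listing

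*SAP*

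**What the plan says.** **Collection.** Protocol 7.5.1 names the end day: "The reporting period for unsolicited AEs is immediately after study vaccine administration on Day 1, continuing through Day 29". Footnote d of the schedule of events, in both documents, narrows collection only after Day 29. From then on the SAP's version covers SAEs, NOCIs and MAAEs; the protocol's version names SAEs and NOCIs. Protocol 3.1 gives a length instead of an end day: "unsolicited safety information for 28 days post-vaccination".

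**Definition.** Protocol 7.1.1 says: "The definition of a treatment emergent AE (TEAE) is an event that occurs after vaccination and within the 28 days after vaccination". It gives no day numbers. SAP 6.4.1.2 repeats this and turns it into a formula: onset day is the AE start date minus the vaccination date plus 1. The rule "An AE is a TEAE if Onset" then takes values from 1 to 28.

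**Reporting.** Protocol 9.5.3 says that all unsolicited AEs during the study are recorded, but it limits the summaries to TEAEs and promises listings of TEAEs. SAP 6.4.1.2 plans tables of TEAEs (any, related, leading to withdrawal), deaths, SAEs, NOCIs and MAAEs. Its three listings cover pre-vaccination AEs, unsolicited TEAEs, and "All post-vaccination SAEs, NOCIs and MAAEs". The summaries and listing in SAP 6.4.1.3 are also limited to TEAEs.

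**Visit.** Protocol 6.1.4 schedules "AE (unsolicited) and SAE evaluation" at the Day 29 visit, which has a window of 3 days either side (Days 26 to 32).

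**The concern.** Safety is the primary objective, and the percentage of subjects with unsolicited AEs within 1 month is one of the primary endpoints. Day 29 is inside the stated reporting period, yet an AE that starts on that day fails the TEAE rule. Because almost all unsolicited AE output depends on that rule, the AE is missing from the listings as well as from a table. A reader of the study report could not tell that it had been collected.

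The SAP implies, but does not say, that the 1-month endpoint comes from the table of any unsolicited TEAE. If so, the endpoint is counted over one day less than the reporting period. The phrase 1 month does not justify stopping at Day 28. SAP 3.3 equates it with Day 29 for the blood sample, and SAP 5.2 converts a month to 30.4375 days.

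**Working it through.** **1. Day count.** For vaccination date D, an AE that starts on D has onset D − D + 1 = 1. An AE that starts on D + 27 has onset 28 and is a TEAE. One that starts on D + 28 has onset 29, which exceeds 28, so it is not a TEAE. Day 29 is D + 28. The SAP window therefore has 28 calendar days and ends on Day 28.

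**2. Two ways to read 28 days.**
- *Inclusive, vaccination day as the first day:* Days 1 to 28. The SAP formula fits the length but not the end day named in Protocol 7.5.1. The 7-day solicited window is counted this way (Protocol 5.10; SAP 6.4.1.1, Day 1 to Day 7).
- *Elapsed days:* 28 days after Day 1 is Day 29. The protocol's length and its named end day agree, and the SAP bound is one day short. The 211-day maximum in Protocol 3.3 fits this count: 30 + 1 + 180 = 211.

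On either reading, Day 29 is collected and not reported. The visible text states no counting rule. Protocol Figure 2, which summarizes the reporting periods, was not available to this review.

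**3. Tracing a Day 29 AE through the output.** Take a fully dated AE with onset 29 that is not fatal and is not an SAE, NOCI or MAAE. It fails the three TEAE tables, the death table and the three 6-month tables in SAP 6.4.1.2. It is not a pre-vaccination AE, a TEAE, or an entry in the third listing. SAP 6.4.1.3 admits only TEAEs. It appears in none of them.

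**4. Partial dates.** SAP 6.1.6 imputes a missing day as the dose date (same month as the dose) or the first of the month (later month). Of the 337 vaccination dates in 2022 for which Day 29 falls in the same year, 326 give an imputed onset of 28 or less. The 11 exceptions are those where Day 29 is itself the first of a month. The gap therefore concerns mainly fully dated AEs.

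**5. Size.** The documents give neither an AE rate nor a spread of visit days, so both are assumptions. Let p be the proportion with at least one unsolicited AE by Day 29. With a constant hazard, the proportion still free of AEs after day d is S(d) = (1 − p)^(d/29). The loss is S(28) − S(29), the share of subjects whose first AE falls on Day 29. For p = 0.05: 0.95^(28/29) − 0.95 = 0.00168.

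If visits spread evenly over Days 26 to 32 and AEs are recorded only through Day 29, 4 of the 7 visit days (29 to 32) reach Day 29, and the loss is multiplied by 4/7.

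| p | Loss, all observed through Day 29 (points) | Of 200 subjects | Loss, visits spread (points) | Of 200 subjects |
|---|---|---|---|---|
| 5% | 0.168 | 0.34 | 0.096 | 0.19 |
| 10% | 0.328 | 0.66 | 0.187 | 0.37 |
| 20% | 0.618 | 1.24 | 0.353 | 0.71 |
| 30% | 0.866 | 1.73 | 0.495 | 0.99 |

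These figures size the endpoint, not the listing, because a subject with an earlier TEAE may also have an AE on Day 29. If AEs recur at the same hazard, the expected number starting on Day 29 among 200 subjects is 200 × [−ln(1 − p)]/29. This gives 0.35 at p = 5% and 2.46 at p = 30%, less any that appear in the other listings.

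**The case against.** The best defence is that the SAP formula follows a recognised count. Counted inclusively, 28 days is Days 1 to 28, just as 7 solicited days are Days 1 to 7. Protocol 9.5.3 itself chose to summarize and list only TEAEs, so that restriction is not an SAP invention. Both points are correct. They explain the bound and the restriction, but they do not remove the named end day in Protocol 7.5.1 or give a Day 29 AE a place in the output. The synopsis says in general terms that calculated fields will be listed. That does not commit to a listing of these AEs, and the SAP's own set of listings leaves them out.

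A reader might infer two stronger claims that the documents do not support:
- *That the protocol contradicts itself.* Counted as elapsed days, its 28 days and its Day 29 agree. What is missing from the visible text is a counting rule, and Figure 2 may supply one.
- *That AEs starting on Days 30 to 32 and found at a late visit are wrongly kept out of the TEAE tables.* It is tempting, because Protocol 9.2 says: "The Treatment period begins at the time of study vaccine administration and extends through the Day 29 visit". But those days lie outside the protocol's TEAE definition on either count, and beyond the reporting period in 7.5.1. Nor are the documents silent on recording, since Protocol 9.5.3 says that all unsolicited AEs during the study are recorded. The only gap for those days is the missing listing.

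It is also fair to say that a bound of 29 is a choice. A listing alone would end the non-reporting.

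**Conclusion.** The point holds for Day 29. The TEAE bound stops one day before the named end of collection, and a fully dated Day 29 AE that is not fatal and is not an SAE, NOCI or MAAE enters no planned unsolicited AE table or listing.

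The effect on the 1-month percentage is at most 0.17 to 0.87 points (0.34 to 1.7 of 200 subjects), and 0.10 to 0.49 points with visits spread evenly over Days 26 to 32. Both ranges assume a constant hazard, 5% to 30% of subjects with an AE by Day 29, and complete start dates. They affect the endpoint only if it is taken from the TEAE table.

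The rule is the same in all four arms, the endpoint is descriptive, and no decision rule uses it. The documents give no ground for inferring a distorted comparison between arms. The solicited endpoints and the 6-month SAE, NOCI and MAAE endpoints are unaffected. Severity: minor.

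**What to change.** Before database lock:

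1. In SAP 6.4.1.2, change the upper bound of the TEAE rule from 28 to 29, to match the reporting period in Protocol 7.5.1. Add one sentence stating that 28 days after vaccination means through Study Day 29.
2. Add a by-subject listing of all post-vaccination unsolicited AEs regardless of TEAE status. This also shows any Day 30 to 32 onsets recorded at late visits.

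No new data are needed. The costs are a slightly higher reported AE rate, a day count that differs from the solicited convention (Days 1 to 7), and incomplete ascertainment of Day 29 for subjects seen on Days 26 to 28, because the later calls cover only SAEs, NOCIs and MAAEs. If the sponsor prefers to keep 28, the second step alone ensures that no collected AE goes unreported.
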